14.3 Final Analysis Plan

14.3.1 Analysis of Primary Endpoints

Adverse events will be reported using frequency tables. Confidence intervals will be constructed using exact statistical methods (such as exact binomial confidence interval) due to small sample size.

14.3.2 Analysis of Secondary Endpoints

Median radiation treatment time and median number of dose delays due to toxicity will be reported. CLR 131 tumor uptake via SPECT/CT imaging and Monte Carlo calculations will be reported. Quality of life measures (including swallow function assessed by DIGEST scale and

QOL assessed by MDADI score) will be analyzed using frequency tables and confidence intervals constructed using exact statistical methods (such as exact binomial confidence interval) or summary statistics. Comparison of continuous and categorical QOL measures before and after treatment will be described using summary statistics and analyzed using the Wilcoxon signed rank test and McNemar's test, respectively. ORR will be reported as a proportion with an exact confidence interval. Stimulated salivary flow will be reported before and after treatment using summary statistics.

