3.2 Study Outcome Measures

3.2.1 *Primary*

- Incidence of adverse events assessed using Common Terminology Criteria for Adverse Events (CTCAE) version 5.0

3.2.2 *Secondary*

- Median radiation treatment time and median number of dose delays due to toxicity
- CLR 131 tumor uptake via SPECT/CT imaging and Monte Carlo calculations
- Overall response rate (ORR) defined as the proportion of subjects who experience either a partial response or complete response within 6 months post completion of EBRT as measured by standard of care imaging (e.g. CT, MR, PET-MR)
- Swallow function assessed by Dynamic Imaging Grade of Swallowing Toxicity (DIGEST) scale
- Quality of life (QoL) assessed by MD Anderson Dysphagia Inventory score (MDADI)
- Salivary flow rate related quality of life assessed by stimulated salivary flow

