4 STUDY DESIGN

This is a Phase 1, single center, dose escalation and dose expansion study of subjects with locoregionally recurrent head and neck cancer who may also have distant metastatic disease. All subjects will receive a dosimetry test dose of CLR 131 (flat dose of 15 mCi) to establish drug uptake by the tumor.

Subjects who have tumor uptake of the CLR 131 dosimetry test dose as determined on SPECT/CT imaging by the study radiologist will be eligible to participate on the treatment portion of this clinical trial. Any subject who demonstrates tumor uptake of CLR 131 by SPECT/CT imaging after the test dose will continue to participate in the treatment portion of the study. Up to six participants who do not demonstrate tumor uptake of CLR 131 by SPECT/CT will also continue with the treatment portion of the study. Based on prior experience of subjects receiving CLR 131, 75 % of eligible subjects are estimated to demonstrate CLR 131 uptake within their tumors.

Subjects showing uptake will receive a cumulative tumor dose of 60-70 Gy using personalized dose calculation of CLR 131 (via Monte Carlo) combined with external beam radiation. If the Monte Carlo dose estimate for any subject is greater than 60 Gy for the 2 doses of CLR 131 (highly unlikely based on preliminary data), then no additional external beam dose will be administered.

All subjects will start thyroid-protection medication the day prior to the CLR 131 dosimetry test dose and will continue to take thyroid protection medication for 14 days after the last CLR 131 dose.

Treatment Plan

Enrollment will start at dose level 1. Subjects will receive 2 doses of CLR 131 intravenously with the first dose on day 1 followed by the second dose on day 8. The dose of CLR 131 will be based on the dose escalation schema.

Dose Escalation Schema	
Dose Level	Doses** of CLR 131
-1*	12.5 mCi/m ²
1	15.6 mCi/m ²
2	18.75 mCi/m ²

*Dose level -1 is the de-escalation dose. The first four patients will be given Dose 1. Dose -1 will only be used if toxicities warrant de-escalation.

** Dose level listed is administered first on day 1 and again on day 8.

SPECT/CT imaging will be performed on days 2, 3, 4-6, and 7-8 of the treatment period to visualize and quantitate the biodistribution of CLR 131. Using the SPECT/CT imaging scans, the [name] lab will perform the Monte Carlo calculations to predict absorbed dose of CLR 131 to tumors and normal structures.

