6.8 External beam radiation therapy (EBRT)

External beam radiation therapy will be used in combination with CLR 131 infusions to deliver a total dose of 60-70 Gy to the recurrent tumor in subjects determined by study radiologist to exhibit uptake of CLR 131.

The standard of care radiation therapy for this patient population is 60-70 Gy absorbed dose, irrespective of radiation delivery. Therefore, as long as the SOC radiation dose parameters are met, EBRT described in 6.8 is considered within standard of care. The total dose (60-70 Gy) delivered to the recurrent tumor will be at the discretion of the treating Radiation Oncologist.

6.8.1 *Dose specifications and target definition*

The recurrent gross tumor volume (rGTV), as defined by diagnostic imaging including CLR 131 uptake imaging and physical exam findings, will receive daily fractions of 2.0-2.5 Gy. The rGTV

will undergo a geometric expansion of 3-5 mm to create the recurrent clinical target volume (rCTV), which accounts for coverage of areas at high-risk for harboring subclinical disease. The rCTV can be modified by the treating Radiation Oncologist to account for areas thought to be free of disease (e.g. air space, bone). The rCTV will be expanded by 2-3 mm to create a recurrent planning target volume (rPTV). Elective treatment volumes treated to lower dose are generally discouraged but permitted at the discretion of the treating physician.

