7.2.1.1 Treatment Dose Administration

Subjects who have uptake on SPECT/CT imaging scans are eligible for the treatment portion of the clinical trial. These subjects will be treated and evaluated as follows:

- Vital signs will be collected prior to and 1 hour post CLR 131 infusion
- On day 1 of the treatment period, CLR 131 will be administered through a freely running peripheral IV catheter via a slow infusion of approximately 30 minutes duration. The dose of CLR 131 will be calculated for each subject based on total BSA (not to exceed 2.5 m²) calculated from actual body weight and height at screening.
- SPECT/CT imaging will be performed on days 2, 3, 4-6, and 7-8.
- A second treatment dose of CLR 131 will be given on day 8.
- CBC with differential and serum chemistries weekly for 12 weeks (beginning at day 1 of first treatment dose)

- Confirm subject is taking thyroid protection medication as directed.
- Adverse event evaluation
- Urine pregnancy test for WOCP (within 24 hrs prior to each CLR 131 dose)

7.2.1.2 External beam radiation therapy (EBRT) (approximately 7-14 days after the last CLR 131 treatment dose)

Based on the calculated absorbed dose of CLR 131 to the specific targeted tissue, the subject will undergo standard of care EBRT to complete the designated radiation dose outlined in the re-irradiation plan.

An EKG will be performed on the first day of the SOC EBRT. During the course of EBRT, subjects will be evaluated for any adverse events.

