14.2 Sample Size Considerations

An mTPI-2 design, an extension of modified toxicity probability interval (mTPI-2), will be used to identify the MTD using cohorts of 4 subjects and up to 3 dose levels of CLR 131 (Ji *et al.*, 2007; Ji & Wang, 2013). The first 4 subjects will be treated at Dose Level 1. The maximum number of subjects treated at a dose level will be 8, with one exception: if 1 out of 8 subjects experiences a DLT at Dose Level 1, the study team will consider the possibility of treating 2 additional subjects at Dose Level 1. The trial can be monitored using columns 4 and 8 of [Table 3](#) below, which contains the dose-escalation rules. Dose escalation will not be confirmed until all subjects in cohort recover to non-DLT levels or meet the criteria above. If 0 out of 4 subjects experiences a DLT at Dose Level 2, the study will move directly to the expansion phase.

Dose Level	Doses* of CLR 131
-1	12.5 mCi/m ²
1**	15.6 mCi/m ²
2	18.75 mCi/m ²

*Dose level listed is administered on first on day 1 and again on day 8.

**The first 4 subjects will be treated at dose level 1. Dose level -1 will be used as a de-escalation dose.

Table 3: Dose escalation rules

	1	2	3	4	5	6	7	8	9	10
0	E	E	E	E	E	E	E	E	E	E
1	D	D	D	S	S	S	S	S	S	E
2		DU	DU	D	D	D	S	S	S	S
3			DU	DU	DU	DU	D	D	D	D
4				DU	DU	DU	DU	DU	DU	D
5					DU	DU	DU	DU	DU	DU
6						DU	DU	DU	DU	DU
7							DU	DU	DU	DU
8								DU	DU	DU
9									DU	DU
10										DU

Column indicates the number of subjects treated. Row indicates the number of subjects with DLTs. **E**: Escalate to the next higher dose; **S**: Stay at the same dose; **D**: De-escalate to the previous lower dose; **DU**: De-escalate to the previous lower dose and the current dose will never be used again in the trial; sample size = **10**, target toxicity probability = **0.2**, epsilon 1 =**0.1**, epsilon 2 =**0.1**.

The number of participants treated in the expansion cohort is dependent on the number of participants treated at the MTD in the dose escalation phase using the the mTPI-2 design. Up to 12 subjects will be treated at the MTD. Statistical analysis for outcomes is based on participants treated at the MTD, including dose escalation patients treated at the MTD.

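### With 12 subjects the median number of toxicity delays is 0 unless at least 6 are delayed, and raw median treatment time mixes delay with prescription

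*Combined protocol and SAP*

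**What the plan says.** Section 14.3.2 gives one sentence to these outcomes: "Median radiation treatment time and median number of dose delays due to toxicity will be reported". Section 3.2.2 lists the same pair among the secondary outcome measures, but no objective in section 3.1.2 corresponds to it. Neither section defines treatment time or dose delay, and neither asks for a range, a proportion, an interval or a comparison with the planned course.

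The number of subjects comes from section 14.2: "Up to 12 subjects will be treated at the MTD", and "Statistical analysis for outcomes is based on participants treated at the MTD, including dose escalation patients treated at the MTD".

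The length of the external beam course is set subject by subject:

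- Section 6.8: "The total dose (60-70 Gy) delivered to the recurrent tumor will be at the discretion of the treating Radiation Oncologist".
- Section 6.8.1: the recurrent gross tumor volume "will receive daily fractions of 2.0-2.5 Gy".
- Section 7.2.1.2: once the absorbed dose from CLR 131 is known, "the subject will undergo standard of care EBRT to complete the designated radiation dose outlined in the re-irradiation plan".
- Section 4: if the estimate for CLR 131 alone exceeds 60 Gy, "then no additional external beam dose will be administered". The protocol regards this case as very unlikely.

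**The concern.** These two medians are the only planned summaries of how the radiation course was delivered, and each can hide what a reader would look for.

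A median of a count stays at 0 until about half the subjects have a non-zero value. With so few subjects, a sizeable minority could be delayed for toxicity and the reported figure would be the same as if nobody had been.

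Raw treatment time depends on how many fractions were prescribed as well as on interruptions. Section 2.2 hypothesises that CLR 131 lowers the EBRT dose needed. If it does, courses shorten by design, and a short median time could be misread as good tolerance of the combination.

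**Working it through.** The plan states no expected delay rate, median or precision for these outcomes, so there is no figure of its own to reproduce.

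**1. When the median count is 0.** With n = 12 (section 14.2) the median is the mean of the 6th and 7th ordered values. If k subjects have at least one delay, the lowest 12 − k values are 0. Both middle values are 0 when 12 − k ≥ 7, that is, when k ≤ 5. At k = 6 the 7th value is at least 1 and the median is at least 0.5. So 0/12 and 5/12 (5/12 = 42%) give the same summary. This step needs no assumed rate.

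**2. How often that happens.** Let p be the chance that a subject has at least one toxicity delay, with subjects independent. Then P(median = 0) = Σ C(12, k) p^k (1 − p)^(12−k), summed over k = 0 to 5. The values of p are assumptions. Smaller n is shown because 12 is a maximum; the median is then 0 for k ≤ 4 (n = 10) or k ≤ 3 (n = 8).

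| Assumed p | n = 12 | n = 10 | n = 8 |
|---|---|---|---|
| 0.20 | 98.1% | 96.7% | 94.4% |
| 0.30 | 88.2% | 85.0% | 80.6% |
| 0.40 | 66.5% | 63.3% | 59.4% |
| 0.50 | 38.7% | 37.7% | 36.3% |

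For n = 12 the probability is at least 95% only if p is about 0.245 or less, and it falls to 50% at p = 0.46.

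**3. How far the prescription alone moves treatment time.** Fractions = (total dose − CLR 131 dose) / fraction size, rounded up. Calendar days assume 5 fractions a week from a Monday with no interruption. Total dose and fraction size come from sections 6.8 and 6.8.1. The CLR 131 doses are assumptions, since the documents give none.

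| Assumed CLR 131 dose | Shortest course | Longest course |
|---|---|---|
| 0 Gy | 60/2.5 = 24 fractions, 32 days | 70/2.0 = 35 fractions, 47 days |
| 10 Gy | 50/2.5 = 20 fractions, 26 days | 60/2.0 = 30 fractions, 40 days |
| 20 Gy | 40/2.5 = 16 fractions, 22 days | 50/2.0 = 25 fractions, 33 days |

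At a fixed CLR 131 dose the spread is 47 − 32 = 15, 40 − 26 = 14 or 33 − 22 = 11 days. For one prescription (70 Gy at 2.0 Gy), a CLR 131 dose of 20 Gy instead of 0 shortens the course by 47 − 33 = 14 days, whatever the toxicity.

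**4. Effect on the median itself.** The ranges in step 3 are extremes between individuals, so a simulation was used to look at the median. It drew total dose and fraction size uniformly over their stated ranges; delays, where they occurred, lasted 1 to 7 days. With no CLR 131 contribution the median planned course was 39 days, and delaying 30% of subjects raised it to 40. Drawing the CLR 131 dose uniformly from 0 to 20 Gy, with no delays, lowered it to 33. With the same 30% delayed it was 36, still below the 39 days seen with neither. The distributions are illustrative.

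**5. What a proportion would show.** Clopper-Pearson 95% limits for x of 12 are the 2.5% point of Beta(x, 13 − x) and the 97.5% point of Beta(x + 1, 12 − x). They give 0/12 = 0% (0 to 26.5%), 4/12 = 33% (9.9 to 65.1%) and 5/12 = 42% (15.2 to 72.3%). The planned median is 0 in all three.

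**The case against.** The strongest reply is that little depends on these medians. Safety and tolerability of the combination is the primary objective (section 3.1.1). It is measured by CTCAE adverse events, assessed weekly during EBRT (section 8.1.11) and reported in frequency tables with exact intervals (section 14.3.1). Swallowing, MDADI and salivary flow add further information on radiation effects. Serious intolerance would not be hidden. A reader might infer that the two medians are the only evidence on tolerability, or that neither says anything about it. The documents support neither inference: a non-zero median count would be informative, and raw time does include delays.

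A reader might also infer that the median count is bound to be 0. Without a delay rate in the documents that cannot be said. Section 11.3.2 expects Grade 3 mucositis and dermatitis from EBRT, so a high rate cannot be excluded, and at an assumed 50% the median is more likely to be non-zero than 0. Nor is a median of 0 a statement that no delays occurred.

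It is also fair to say that dose delay may not mean EBRT at all, because section 4 discusses delayed CLR 131 dosing; that a single-arm description of course length is not wrong merely because it depends on the prescription; and that naming a median does not forbid reporting more.

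What stands after this is narrower. Adverse event tables show which events occurred, not whether radiation was interrupted. Section 11.1 records the action taken for each event, but no analysis of it is planned. The insensitivity in step 1 and the mixing in step 3 do not depend on any assumed delay rate.

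**Conclusion.** The point holds as a minor weakness in a descriptive secondary outcome. With 12 subjects the median delay count cannot distinguish 0% from 42% delayed. The chance that it reads 0 runs from 98% to 39% as the assumed per-subject rate goes from 20% to 50%. Raw treatment time can differ by about 11 to 15 days between subjects through total dose and fraction size alone, and by more when the CLR 131 contribution differs. A shorter median is therefore not evidence of better tolerability.

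This rests on three assumptions: independent subjects with a common delay rate, five fractions a week, and dose delay referring at least in part to EBRT. The documents do not support a claim that the median will almost certainly be 0, or that tolerability goes unmeasured. No sample size, error rate, dose-finding rule or primary conclusion changes.

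**What to change.** In section 14.3.2:

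1. State whether dose delay covers EBRT, CLR 131 or both, and define treatment time.
2. Add the number and percent of subjects with at least one delay attributed to toxicity, with an exact 95% interval (for example 4/12 = 33%, 10 to 65%). Exact intervals are already the plan's method for adverse events and response rate.
3. Add actual minus planned EBRT days, or their ratio, with planned days taken from the approved treatment plan. List separately any subject who receives no EBRT, for whom the ratio is undefined, or who stops early, for whom the difference can be negative.
4. Keep both medians, with their range, as extra lines.

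The cost is a few more descriptive lines. The documents do not say that planned fractions and the reason for each delay are already collected, so both should be added to the case report form if they are missing. Attribution to toxicity needs a physician's judgement as well as fraction dates.

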2.2 Rationale for a clinical study using CLR 131 in combination with EBRT

Locoregional recurrence in HNC represents a significant challenge. Approximately 50 % of HNC patients will experience loco-regional disease recurrence following initial therapy that commonly includes primary or postoperative radiation. Although some recurrent HNC patients can experience long-term tumor control following re-irradiation, this approach must be considered with great caution due to the risk of severe injury to normal tissue structures that maintain long-term recall from the prior radiation exposure.

Several studies have specifically examined the role of re-irradiation in HNC with general conclusions that there is considerable risk for high-grade toxicities (including death), but a defined opportunity for long-term survival (2 years) in approximately 10-20% of patients (A. M. Chen *et al.*, 2011; Dawson *et al.*, 2001; De Crevoisier *et al.*, 1998; Hehr *et al.*, 2005; Hoebers *et al.*, 2011; Kasperts *et al.*, 2005; Kramer *et al.*, 2005; Langer *et al.*, 2007; Mendenhall *et al.*, 2008; Nag *et al.*, 1998; Salama *et al.*, 2006; S. Spencer *et al.*, 2003; S. A. Spencer *et al.*, 2001; Stevens *et al.*, 1994).

Selection of patients who would most likely benefit from HNC re-irradiation remains an area of active investigation. Efforts to reduce the acute and long-term tissue injury profile by radiation with highly conformal techniques are clearly important in the retreatment setting. With the use of CLR 131, the dose of external beam radiation therapy can potentially be reduced or more precisely targeted, which serves to limit high dose radiation therapy to normal tissues in the head and neck.

The aim of this clinical trial is to evaluate the use of the novel radioisotope CLR 131 as a modality to provide "internal radiation" to recurrent disease in combination with EBRT. This combination regimen would be intended to provide definitive treatment of recurrent head and neck cancer by delivering radiation to HNC cells through CLR 131 uptake followed by the more traditional EBRT. We hypothesize that CLR 131 will reduce the overall dose of EBRT required for retreatment, and minimize the acute and long-term tissue injury that is commonly associated with standard reirradiation treatment plans.

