2.2.1 Hypothesis

The hypothesis of this clinical trial is that reduction of the dose of external beam radiation therapy, when given in combination with CLR 131, will be safe and tolerable while maintaining favorable tumor response rates and diminishing the adverse impact of radiation treatment on subject specific symptoms, such as quality of life, salivary flow and swallowing function.

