14 STATISTICAL CONSIDERATIONS

14.1 Study Hypotheses

Reducing the dose of external beam radiation therapy, when given in combination with CLR 131, will be safe and tolerable while maintaining favorable tumor response rates and diminishing the adverse impact of radiation treatment on subject specific symptoms, such as quality of life, salivary flow and swallowing function.

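### The plan hypothesizes that CLR 131 allows a lower external beam dose, but no planned outcome or analysis reports the external beam dose delivered or how far it was reduced

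*Combined protocol and SAP*

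**What the plan says.** - **Hypotheses.** Section 2.2 states "We hypothesize that CLR 131 will reduce the overall dose of EBRT required for retreatment". Section 14.1 states "Reducing the dose of external beam radiation therapy, when given in combination with CLR 131, will be safe and tolerable", with tumor response maintained and less harm to quality of life, saliva and swallowing. Section 2.2.1 says the same.
- **Outcomes.** Section 3.2 lists adverse events as primary. The secondary outcomes are treatment time and number of toxicity delays, CLR 131 uptake with Monte Carlo calculations, overall response rate (ORR), DIGEST, MDADI and stimulated salivary flow.
- **Analyses.** Section 14.3.1 says "Adverse events will be reported using frequency tables". On EBRT, Section 14.3.2 says only "Median radiation treatment time and median number of dose delays due to toxicity will be reported".
- **How EBRT is set.** Sections 4 and 7.2.1.2 have EBRT complete the designated dose after the calculated CLR 131 absorbed dose is taken into account. Section 6.8 leaves the total, within 60-70 Gy, to the treating radiation oncologist. Section 6.8.1 allows fractions of 2.0-2.5 Gy.
- **Who is analyzed.** Section 14.2: "Statistical analysis for outcomes is based on participants treated at the MTD, including dose escalation patients treated at the MTD", up to 12 subjects. Section 4: "Up to six participants who do not demonstrate tumor uptake of CLR 131 by SPECT/CT will also continue with the treatment portion".
- **Response assessment.** Section 9 assesses response in subjects who receive a treatment dose, then limits those with inadequate uptake after the test dose to safety follow-up.

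**The concern.** The premise under test is a reduced EBRT dose. If the plan is followed exactly, the report will give adverse event rates, an ORR and functional results without saying how much EBRT those subjects received or were spared. A tolerable safety profile after a large reduction means something different from the same profile after almost none. The hypothesis in Section 2.2, that CLR 131 lowers the EBRT dose required, has no reported measure. The reduction will also vary between subjects who are pooled, because CLR 131 uptake varies and some treated subjects may show none on the test-dose scan. CLR 131 uptake is to be reported, but nothing places it beside adverse events or response.

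**Working it through.** The plan states no figure to reproduce. The check is whether the planned outputs yield the EBRT dose or its reduction.

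**1. Hypothesis against outputs.**
- Safe and tolerable: adverse event tables. Covered.
- Response maintained: ORR with exact interval. Covered descriptively.
- Quality of life, saliva, swallowing: MDADI, stimulated flow, DIGEST. Covered.
- EBRT dose reduced: nothing in Section 3.2 or 14.3. EBRT dose appears only as a treatment instruction (Sections 4, 6.8 and 7.2.1.2).

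**2. Can EBRT dose be recovered from the CLR 131 dose?** EBRT = T - C, where T is the designated total (60-70 Gy, Section 6.8) and C is the CLR 131 dose credited. The documents give no expected C, so these values are illustrative.
- C = 10 Gy: EBRT 50-60 Gy
- C = 20 Gy: EBRT 40-50 Gy
- C = 30 Gy: EBRT 30-40 Gy

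A 10 Gy range remains whatever C is.

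**3. Can it be recovered from treatment time?** Fractions n = (T - C)/f, rounded up, with f = 2.0-2.5 Gy. Assuming five fractions a week and a Monday start, calendar days = n + 2 × (weeks begun - 1).
- No credit, 60 Gy at 2.5: n = 24, 24 + 2 × 4 = 32 days
- No credit, 70 Gy at 2.5: n = 28, 28 + 2 × 5 = 38 days
- No credit, 60 Gy at 2.0: n = 30, 30 + 2 × 5 = 40 days
- No credit, 70 Gy at 2.0: n = 35, 35 + 2 × 6 = 47 days

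The spread is 47 - 32 = 15 days before any reduction or toxicity. Now compare two subjects, each with T = 60 and f = 2.0.
- No credit, no break: 40 days.
- C = 20: n = 20, 20 + 2 × 3 = 26 days planned. With a 14-day toxicity break, 26 + 14 = 40 days.

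The planned outcome gives both the same time. Delivered minus planned days gives 40 - 40 = 0 and 40 - 26 = 14. The separate delay outcome would record none and one, but it counts delays rather than days and is summarized as its own median.

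**4. Pooling and the ORR denominator.** Let k be the number of treated no-uptake subjects at the maximum tolerated dose (MTD). The documents cap k at 6 and do not give its value. Section 5.5.1 requires all CLR 131 doses and one assessment for efficacy, with no uptake condition. That rule and the first statement in Section 9 include the k subjects; the second statement in Section 9 excludes them. Suppose 12 subjects meet Section 5.5.1 and three respond, all with uptake.
- Included: 3/12 = 25% (exact 95% interval 5.5% to 57.2%)
- Excluded, k = 3: 3/9 = 33%
- Excluded, k = 6: 3/6 = 50% (11.8% to 88.2%)

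**5. What a display by uptake can show.** With zero events, the exact two-sided 95% upper limit is 1 - 0.025^(1/n): 26% for n = 12, 34% for n = 9, 71% for n = 3. It can only describe.

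**The case against.** The strongest reply is that reduced EBRT is the intervention, not the endpoint. Section 3.1 has no objective to quantify the reduction. Safety, response, quality of life, saliva and swallowing each have an outcome and an analysis, and the explicit claim that CLR 131 lowers the required dose sits in the rationale. The study is a small, uncontrolled phase 1, uptake and CLR 131 dose will be reported, and EBRT doses can be taken from treatment records at any time. Treatment time is not said to isolate toxicity, since delays are counted separately.

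Much of this stands. A reader might infer that the plan does not address its hypothesis at all; that goes too far, because most of its components are measured. What does not fall away is that an intervention defined by a reduction needs the reduction reported, and the plan makes no such commitment.

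Three further inferences should also be resisted.
- *That the EBRT credit for treated no-uptake subjects is undefined.* Section 8.1.12 gives them the same treatment-dose imaging and Monte Carlo prediction, and Sections 4 and 7.2.1.2 set EBRT from the calculated absorbed dose. There is therefore no basis for assuming zero credit and computing a diluted average reduction.
- *That 75% uptake means about 3 of 12 MTD subjects lack it.* Uptake is an inclusion criterion with a capped exception (Section 5.2, criterion 7), and the cap covers every dose level.
- *That subjects given one treatment dose blur the ORR.* Section 5.5.1 removes them from efficacy; they affect safety only.

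**Conclusion.** The concern holds as a reporting gap. The EBRT dose delivered and its reduction are not among the planned outputs and cannot be worked out from them. A known CLR 131 dose leaves a 10 Gy range for EBRT, and equal treatment times can hide a 20 Gy difference in EBRT. The first result needs only the protocol's 60-70 Gy range. The second uses an illustrative 20 Gy credit, an illustrative 14-day break and a five-day week. The gap itself depends on none of these values.

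The ORR denominator conflict in Section 9 is a separate defect. Its effect depends on how many no-uptake subjects were treated at the MTD, anywhere from 0 to 6.

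Neither point affects dose decisions, safety monitoring or sample size. Reporting the reduction would not create a comparator. The change is worth making because the reduction is the study's premise and the remedy is cheap.

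**What to change.** The Protocol Summary gives accrual as closed, so the changes concern reporting only.

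1. In Sections 3.2.2 and 14.3.2, add a per-subject listing, with median and range, of designated total dose, CLR 131 dose credited, EBRT dose and fractions delivered, and reduction from the designated dose. Show it beside adverse events and response, flagged by uptake status. Keep the pooled MTD tables and call the uptake display descriptive.
2. Report treatment time as delivered minus planned days, where planned means the EBRT course prescribed after the CLR 131 credit.
3. Amend Section 9 so that its safety-only sentence applies to no-uptake subjects who receive no treatment dose. Treated no-uptake subjects who meet Section 5.5.1 then count in the ORR.

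The cost is wording in three sections and one listing for up to 12 MTD subjects from treatment records. Section 18.3 does not name EBRT dose among the data held, so it may need to be extracted. The listing may also show that some subjects had little EBRT reduction.
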